## **APPENDIX B: VISIT SCHEDULE—Monthly Group—Month 13 to Month 24 (Continued)**

- C. Significant medical/surgical history from the previous 5 years. Anti-VEGF treatments (fellow eye) and invasive ocular procedures performed within the past 5 years and while on study should also be recorded. Any history of tobacco use should be recorded.
- D. Obtain prior to fluorescein angiography and before study drug administration.
- E. At screening, serum pregnancy should be performed for women of childbearing potential. If positive, subject is not eligible to continue in the study.
- F. Beginning at Day 1, perform the urine pregnancy test for women of childbearing potential at each treatment visit. If positive, perform a serum pregnancy test. If serum test is positive, study drug should not be administered and an early term visit should be completed.
- G. Only subjects that sign the separate consent for the clinical repository and genotyping will have these samples collected. A 14-mL whole-blood sample will be collected at each of the specified visits.
- H. Blood pressure, respiratory rate, heart rate, and temperature. On dosing days, vital signs should be taken predose.
- I. Height and weight should be measured at screening.
- J. Perform assessments prior to dilating the eyes.
- K. In select countries, the MNREAD or Radner Reading Charts should be done during the study visit, prior to dilating the eyes. It should be performed monocularly first, then binocularly.
- L. To be administered by the masked site staff prior to any other assessments performed on that day. In-clinic assessments on the digital application should be completed after completion of all functional tests and quality of life measures prior to dilating the eyes.
- M. At select sites, and for those subjects who decide to participate, the digital applications will be completed on an electronic device and will consist of assessments for visual function and reading speed. Subjects will receive training at Day 1 on the use of the digital applications and the electronic device and will perform the tests using the application in the clinic at Month 1, Month 2, Month 3, Month 6, Month 12, Month 18, and Month 24. Beginning at Day 1, subjects will complete the functional assessments weekly at home. Subjects should be instructed to complete the assessments on the same day each week and at approximately the same time of day each week, if possible.
- N. FAF and SD-OCT images, near infrared reflectance, fluorescein angiograms, and fundus photographs will be performed for the study eye only on days where 'SE' is specified and for both eyes at all other visits as specified in the above schedule and will be sent to the reading center for evaluation (consult the reading center manual for specifics on image capture, processing, and transmission). Images should be captured prior to dosing on dosing days. If a subject misses a study visit or images cannot be obtained at a specific visit, study staff should make every effort to obtain images at the next scheduled visit. If new active CNV is suspected, SD-OCT, FFA, and OCT-A (selected sites) images should be collected and sent to the reading center for analysis.
- O. Postinjection assessments should be performed within 5 minutes after dosing by the unmasked physician or study staff and should include a gross assessment of vision (finger-counting, hand motion, then light perception when applicable). If subject passes gross vision test, the subject may leave the site. If subject fails gross vision test, the tonometry should be performed. IOP should be  $\leq 30$  mm Hg in order for the subject to leave the site. If necessary, antiglaucomatous medication can be given to lower the IOP. If IOP is  $>30$  mm Hg, assessments will continue every approximately 30 minutes from the previous measurement until the subject passes gross vision test and IOP is  $\leq 30$  mm Hg. Note: if the study eye is treated with a ranibizumab or aflibercept injection during the same visit as the study treatment (pegcetacoplan or sham), the treatment with ranibizumab or aflibercept must be performed first. The pre- and post- anti-VEGF IOP values must be measured and recorded on the eCRF.
- P. Starting at Day 1, study subjects will be contacted by study site staff within  $4 \pm 2$  days after each study treatment visit (through Month 3) to collect any information on any safety concerns, decrease in vision, eye pain, unusual ocular events, or any new ocular symptoms in the study eye. If the physician determines that there are any safety concerns, a follow-up visit should be scheduled as soon as possible.
- Q. Record concomitant medications (ie, prescription and over-the-counter medications) used by the patient within 30 days of screening and throughout the subject's participation in the study.
- R. In addition to the time points indicated on the study schedule, OCT-A should be performed at the time of any suspected new active CNV. If new active CNV is confirmed in the study eye, OCT-A should be repeated every 2 months for the study eye.
- S. At select sites only.
- T. Administration of study treatment (pegcetacoplan or sham) can be done on a separate day from the assessment visit if both days fall within the visit window. If this occurs on the randomization visit, then the administration of pegcetacoplan or sham should be done within 3 days of randomization and after approval from the medical monitor. When study treatment administration is on a day other than a study visit, then the only assessment that must be done on the day of study treatment administration is the preinjection IOP.

**APPENDIX C: VISIT SCHEDULE—Every-Other-Month Group—Screening, Day 1 Through Month 12**

	Screening	Treatment														Early Term A
Visit #	1	2	2A	3	4	5	6	7	8	9	10	11	12	13	14	
Day	-28 to -1	1	7	30	60	90	120	150	180	210	240	270	300	330	360	
Week	0	0	1	4	8	12	16	20	24	28	32	36	40	44	48	
Month	0	0	0	1	2	3	4	5	6	7	8	9	10	11	12	
Window (+ or - days)	2	0	1	8	8	8	8	8	8	8	8	8	8	8	8	
Informed Consent/Assign Screening Number	x															
Demographic Data	x															
Inclusion/Exclusion Criteria B	x	x														
Medical/Surgical/Ocular History C	x															
Blood Draw—Safety Labs D,E,F	x	x			x				x						x	x
Urine Sample Collection D,E,F	x	x			x				x						x	x
Urine Pregnancy Test D,E,F		x			x		x		x		x		x		x	
Blood Draw—PK and Complement Profile (C3, CH50, AH50) D,S		x	x	x					x						x	x
Blood Draw—Genotyping (if applicable) D					x											
Blood Draw- Anti-Pegcetacoplan Ab D		x		x	x				x						x	x
Blood Draw for Clinical Repository (if applicable) D,G					x				x						x	x
Vital Signs H	x	x		x	x	x	x	x	x	x	x	x	x	x	x	x
Physical Examination I	x														x	x
BCVA J	x	x		x	x	x	x	x	x	x	x	x	x	x	x	x
LL-BCVA J		x		x	x	x	x	x	x	x	x	x	x	x	x	x
MNREAD or Radner Reading Charts (select countries) J,K		x							x						x	x
Slitlamp Examination	x	x		x	x	x	x	x	x	x	x	x	x	x	x	x
Endothelial Cell Count S		x							x						x	x
NEI VFQ-25 L		x							x						x	x
FRI L		x							x						x	x
Home-Based Digital Applications L,M,S		x		x	x	x			x						x	
Dilated Indirect Ophthalmoscopy	x	x		x	x	x	x	x	x	x	x	x	x	x	x	x

**APPENDIX C: VISIT SCHEDULE—Every-Other-Month Group—Screening, Day 1 Through Month 12  
(Continued)**

	Screening	Treatment														Early Term A
	1	2	2A	3	4	5	6	7	8	9	10	11	12	13	14	
Visit #	1	2	2A	3	4	5	6	7	8	9	10	11	12	13	14	
Day	-28 to -1	1	7	30	60	90	120	150	180	210	240	270	300	330	360	
Week	0	0	1	4	8	12	16	20	24	28	32	36	40	44	48	
Month	0	0	0	1	2	3	4	5	6	7	8	9	10	11	12	
Window (+ or - days)	2	0	1	8	8	8	8	8	8	8	8	8	8	8	8	
IOP Measurement	x	x		x	x	x	x	x	x	x	x	x	x	x	x	x
SD-OCT N	x	x		x	x	x	x	x	x	x	x	x	x	x	x	x
FAF N	x	x			SE		SE		x		SE		SE		x	x
NIR N	x	x			SE		SE		x		SE		SE		x	x
DCFP N	x														x	x
FFA N	x														x	x
OCT-A R, S		x R							x R						x R	x
Study Eye Determination	x															
Randomization		x														
Pegcetacoplan administration or Sham Injection T		x			x		x		x		x		x		x	x
Postinjection Assessment O		x			x		x		x		x		x		x	x
Follow-Up Call P		x			x		x									
Concomitant Medication/Concomitant Ocular Procedures Q	x	x	x	x	x	x	x	x	x	x	x	x	x	x	x	x
Adverse Events	x	x	x	x	x	x	x	x	x	x	x	x	x	x	x	x

Abbreviations: AH50 = alternative pathway of complement functional test; BCVA = best corrected visual acuity; CH50 = classical pathway of complement functional test; CNV = choroidal neovascularization; DCFP = digital color fundus photography; eCRF = electronic case report form; FAF = fundus autofluorescence; FFA = fundus fluorescein angiography; FRI = Functional Reading Independence Index; IOP = intraocular pressure; LL-BCVA = low luminance best corrected visual acuity; MNREAD = Minnesota Low-Vision Reading Test; NEI VFG-25 = National Eye Institute Visual Functioning Questionnaire 25-Item Version; NIR = near infrared reflectance; OCT-A = optical coherence tomography angiography; PK = pharmacokinetics; SD-OCT = spectral domain optical coherence tomography; SE = study eye; Term = termination; VEGF = vascular endothelial growth factor.

Note: All ocular assessments are to be performed for both eyes unless annotated with 'SE' (study eye) in the above schedule. All assessments should be performed on the same day. All study visits should be scheduled and projected based on the Day 1 visit date with the exception of Visit 2a which should be based on the Day 1 dose date.

A. For subjects that discontinue the study early, the early termination assessments should be performed after a minimum of 30 days have passed from the last dosing visit. If a subject reports for a scheduled visit and decides to terminate early prior to dosing, the visit should be considered the early termination visit and all early termination procedures should be performed. At Month 24, all subjects should be offered entry into an open-label study.

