## 8. STUDY PROCEDURES

A study schema is presented below in [Figure 1](#). All randomized subjects will return every month to the clinical site for assessments and additional pegcetacoplan or sham injections according to their randomization scheme until Month 12. From Month 12 onwards, subjects will return to the clinical site based on their randomized treatment schedule (monthly or EOM) and will follow the treatment regimen and assessments outlined in the Visit Schedule until Month 24. In addition, subjects will be contacted via phone by masked study staff 4 ( $\pm 2$ ) days after the first 3 study treatments to collect safety information.

The end of this trial for each subject is defined as when the subject completes their Month 24 study visit, approximately 30 days (monthly treatment group) and approximately 60 days (EOM treatment group) after the last visit at which IP is administered. The period following last dose of IP is sufficient to evaluate the safety of pegcetacoplan based on its half-life in the vitreous; further details can be found in the pegcetacoplan IB. At the end of the 24-month study period, subjects will be offered entry to enroll into a separate open-label study.

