### 11.2. Recording Adverse Events

Adverse events and SAEs will be collected from the signing of the consent form until the last visit or early termination visit, 30 days after the last IP administration for the monthly treatment groups and 60 days after the last IP administration for the EOM treatment groups.

Any events that occur prior to dosing will be categorized as pretreatment events; events occurring after dosing will be recorded as TEAEs (start date of dosing and, therefore, categorization of the event will be dependent on randomization assignment).

For each AE, the investigator will evaluate and report the onset date (and time if applicable), resolution date (and time if applicable), intensity, causality, action taken, serious outcome, and whether or not it caused the subject to discontinue the study.

If possible, the outcome of any AE that caused permanent discontinuation or was present at the end of the study should be reported, particularly if the AE was considered by the investigator to be related to the IP. Subjects experiencing AEs that cause interruption or discontinuation of IP, or those experiencing AEs that are present at the last visit or early termination visit should receive follow-up as appropriate.

All SAEs must be reported to the sponsor/Apellis Safety via eCRF within 24 hours of becoming aware of the event, whether or not the event is deemed treatment-related. If the electronic data capture (EDC) system is not operational (or for paper-based study[ies]), the site must complete the paper SAE form and email to CCI immediately and also within 24 hours of becoming aware of the event. The reported information submitted as a paper SAE must be entered into the EDC system once it becomes operational.

Adverse events will be coded in accordance with the Medical Dictionary for Regulatory Activities (MedDRA). If known, the diagnosis of the underlying illness or disorder should be recorded, rather than its individual symptoms.

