### 12.8. Safety Analyses

Adverse events will be collected from the time of the first study drug administration until a subject completes the study or discontinues prematurely. Treatment-emergent adverse events are defined as those AEs that develop or worsen after the first dose of study medication and up to 30 days beyond the last dose of study medication. The current version of MedDRA will be used to classify all AEs. Treatment-emergent AEs will be summarized by System Organ Class and Preferred Term, in accordance with the MedDRA coding dictionary. The number of subjects reporting each AE Preferred Term will be tabulated for all TEAEs and separately for those considered as related to study treatment by the investigator or designee. Number of subjects reporting SAEs will also be tabulated. Adverse event summaries will be presented for each treatment group separately.

Adverse events will be summarized by MedDRA coding terms, and separate tabulations also will be produced for related AEs (those considered by the investigator as definitively drug related), SAEs, and discontinuations due to AEs. Vital signs data and findings from physical and ophthalmologic examinations will be tabulated for changes over time on study. Laboratory parameters will be summarized for changes across study by using descriptive statistics. Separate summaries will be prepared for systemic (nonocular) and ocular AEs, with events in the study eye and nonstudy eye summarized separately.

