A. For subjects that discontinue the study early, the early termination assessments should be performed after a minimum of 30 days have passed from the last dosing visit. If a subject reports for a scheduled visit and decides to terminate early prior to dosing, the visit should be considered the early termination visit and all early termination procedures should be performed. At Month 24, all subjects should be offered entry into an open-label study.

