### **EXTENDED IP ADMINISTRATION WINDOWS**

In order to allow more flexibility to sites and subjects, and to potentially mitigate missed IP administration, an extended IP administration window can be followed. The extended window can ONLY be used in situations related to COVID-19 restrictions and after medical monitor approval. Footnote “T” of each COVID-19 assessment table below reflects these extended IP options.

Per protocol, the IP administration window is as follows:

- Monthly treatment group: +/- 8 days for the entire study duration
- EOM treatment group: +/- 8 days for the first study year and +/- 16 days for the second study year

During COVID-19 restrictions, the IP administration window can be extended to the following:

- Monthly treatment group: -8 days to +15 days. Note, interval for consecutive injections must be at least 14 days.
- EOM treatment group: -8 days to +30 days for the first study year and -16 days to +30 days for the second study year.

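### An every-other-month subject who withdraws fully can have a compliant early termination visit up to 30 days before the stated 60-day adverse event collection period ends, and no later safety contact is planned

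*Protocol*

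**What the plan says.** Protocol Section 11.2 collects AEs and SAEs from consent to the last visit or the early termination visit. In the same sentence it dates that point at 30 days after the last dose for the monthly groups and "60 days after the last IP administration for the EOM treatment groups". Sections 8 and 8.1.4.2 use the same split for completers; for EOM, Month 24 is "approximately 60 days (EOM treatment group) after the last visit at which IP is administered".

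Footnote A of the visit schedules makes no such split. In both EOM schedules (Appendices C and D), their COVID-19 versions in Appendix K, and the SAP copies (Tables 10, 11, 14 and 15), it says that "the early termination assessments should be performed after a minimum of 30 days have passed from the last dosing visit". The monthly schedules carry the same text. The footnote goes on to say that if a subject attends a scheduled visit and "decides to terminate early prior to dosing, the visit should be considered the early termination visit"; no minimum interval is attached to that sentence.

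Protocol Section 11.8 offers a subject who withdraws completely one early termination visit. The only planned safety calls are made 4 (±2) "days after the first 3 study treatments to collect safety information".

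**The concern.** For monthly subjects the 30-day floor and the 30-day collection period match. For EOM subjects the floor is half the stated period. A site that follows footnote A exactly can close a withdrawing EOM subject's safety record at day 30, with no scheduled contact between then and day 60.

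What could be lost is a new-onset AE or SAE in that interval. Section 10 follows abnormalities that persist at exit, and Section 11.5 follows AEs that already exist; neither looks for new ones. Section 8.1.5 asks sites to bring leavers back where possible, but it schedules no contact. What remains for new events is passive: a spontaneous report by the subject (Section 11.1) and the 24-hour duty to report an SAE once the site is aware of it (Section 11.2).

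**Working it through.** **Inputs.** The collection period after the last EOM dose is 60 days (Section 11.2). The floor for the early termination (ET) visit is 30 days (footnote A). Visit days come from Appendices B to D. Appendix K restates the standard EOM dosing window as +/- "8 days for the first study year and +/- 16 days for the second study year". The temporary COVID-19 window for year 2 runs from minus "16 days to +30 days for the second study year", and from −8 to +30 days in year 1; its use needs medical monitor approval.

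**The plan's own figures, for completers.** EOM: Month 24 minus the last dose at Month 22 = 720 − 660 = 60 days. Monthly: Month 24 minus the last dose at Month 23 = 720 − 690 = 30 days. Both agree with Section 11.2.

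**Early leavers.** Gap = ET day − last dose day. Shortfall = 60 − gap.

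| Route to exit (EOM) | Last dose (day) | ET visit (day) | Gap | Short of 60 |
|---|---|---|---|---|
| 30-day floor | any | dose + 30 | 30 | 30 |
| Stops before dosing, nominal days | 420 | 480 | 60 | 0 |
| Same, year-1 window extremes | 60 + 8 = 68 | 120 − 8 = 112 | 44 | 16 |
| Same, Month 12 to Month 14 extremes | 360 + 8 = 368 | 420 − 16 = 404 | 36 | 24 |
| Same, year-2 window extremes | 420 + 16 = 436 | 480 − 16 = 464 | 28 | 32 |
| Same, temporary COVID-19 window, year 1 | 60 + 30 = 90 | 120 − 8 = 112 | 22 | 38 |
| Same, temporary COVID-19 window, year 2 | 420 + 30 = 450 | 480 − 16 = 464 | 14 | 46 |

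The nominal row has one small exception: Day 1 to Month 2 is 60 − 1 = 59 days, 1 short.

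**Non-dosing visits in year 1.** No dose is due at these visits, so I apply the floor rather than the stop-before-dosing sentence.

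- Month 3 is nominally 90 − 60 = 30 days after the Month 2 dose, so an exit there is 30 short on ordinary timing. Months 5, 7, 9 and 11 follow the same pattern.
- With ±8 days at each end the gap ranges over 30 ± 16 = 14 to 46 days. The floor cuts this to 30 to 46, which is 14 to 30 short.
- Month 1 is nominally 30 − 1 = 29 days after Day 1, one day under the floor. A compliant visit within its window (days 31 to 38) is 30 to 37 days after the dose, which is 23 to 30 short.

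**How many subjects.** The EOM arms plan about 200 + 100 = 300 subjects. Only those who withdraw fully before Month 24 are exposed to the gap. The documents give no withdrawal rate, so the number cannot be computed.

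**The case against.** The best reply is that the texts need not conflict. Thirty days is a floor, so an exit visit on day 60 satisfies both. The 30/60 figures in Section 11.2 match the completer timings and may have been written with completers in mind. Section 12.8 supports that reading: collection runs "until a subject completes the study or discontinues prematurely". The same section defines TEAEs up to 30 days after the last dose in every arm, so a uniform 30-day floor may be deliberate.

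Much of this stands, and it keeps the point minor. It does not remove it, because Section 11.2 names the early termination visit in the same sentence as the 60 days. If collection ends at that visit whenever it occurs, the 60-day figure is not delivered for early leavers. If day 60 governs, no contact is planned to deliver it.

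The 30-day TEAE limit does not settle the matter either. SAP Section 7.1 defines TEAEs with no upper limit, and SAP Section 1 says the SAP supersedes the protocol's analysis plan, so a day-45 event would count if it were recorded. SAP Section 5.6 cuts both ways: it adds 60 days after the last EOM injection to treatment duration, then truncates at early termination.

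A further objection is that the fix reaches few people. Subjects willing to stay in contact are already encouraged to remain in follow-up (Sections 6.5 and 11.8), and those who refuse contact cannot be called. That limits the gain.

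**Conclusion.** The mismatch is real and small. On the standard schedule, a compliant early termination visit can fall 30 days short of the 60 stated for EOM subjects, with no solicited contact afterwards for new events. The figures 32 (standard windows) and 46 (temporary COVID-19 window) are extremes reached only through the stop-before-dosing sentence, where the usual shortfall is nominally zero.

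A reader might go further in three ways that the documents do not support.

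- *Day 60 is pharmacologically necessary.* The documents give no such reason. The dose is 15 mg in both regimens, and Section 8 calls about 30 days sufficient for the monthly groups.
- *The safety comparison is biased.* PEOM and SEOM share the same footnote, and no effect on an endpoint or a treatment comparison is shown.
- *Late events cannot be captured at all.* Spontaneous reports and SAE reporting on site awareness remain; what is missing is a planned question.

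The conclusion assumes that the subject withdraws fully, that the site uses the earliest timing footnote A permits, and that the 60 days in Section 11.2 was meant to apply to early leavers as well as completers. It is a cheap improvement of low severity.

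**What to change.** Leave the timing of the early termination visit as it is. Add one sentence to footnote A of the EOM schedules (Appendices C and D, their COVID-19 versions in Appendix K, and SAP Tables 10, 11, 14 and 15): if the early termination visit falls before day 60 after the last dose, a subject who agrees to further contact is telephoned on day 60 to record new AEs and SAEs.

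The cost is the footnote edit and one call per EOM leaver who exits before day 60; some will decline. No new procedure is needed, because the protocol already collects safety information by telephone after the first three treatments (Section 8) and for visits missed under COVID-19 restrictions (Appendix K).
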